2. LIST OF ABBREVIATIONS

See Medicine Glossary:
<http://glossary>

Term	Definition / description
AE	Adverse event
AESI	Adverse event of Special Interest
ADS	Analysis Dataset
ALK	Alkaline Phosphatase
ALT	Alanine Aminotransferase
AST	Aspartate Aminotransferase
AUC τ ,ss	Area under the Plasma Concentration-Time Curve at Steady State
AUC τ ,ss_D	Dose normalized AUC τ ,ss
BI	Boehringer Ingelheim
bid	bis in die
	
CDG	Customized Drug Groupings
cHP	Chronic Hypersensitivity Pneumonitis
CL/F _{ss}	Apparent Clearance of the Analyte in the Plasma at Steady-State following extravascular multiple dose administration
C _{max}	Maximum Concentration in Plasma
C _{max,ss}	Maximum Measured Concentration of the Analyte in Plasma at Steady State
CT	Computed Tomography
CTD	Connective Tissue Disease
CTP	Clinical Trial Protocol
CTR	Clinical Trial Report
Δ	Delta, i.e. difference
DBL	Database Lock
D _{LCO}	Diffusing Capacity of the Lung for Carbon Monoxide
DMARDs	Disease-Modifying Anti-Rheumatic Drugs
DRC	Disease Review Committee
DV domain	SDTM Protocol Deviations domain model
eCRF	electronic Case Report Form
EDMS	Electronic Document Management System

Term	Definition / description
EMA	European Medicines Agency
EOT	End of Treatment
FPI	First patient in (= first patient randomised)
FVC	Forced Vital Capacity
g	Gramm
	
Hb	Haemoglobin
HRCT	High-Resolution Computer Tomography
ICH	International Conference on Harmonisation
ILD	Interstitial Lung Disease
INR	International Normalized Ratio
iPD	Important Protocol Deviation
IRT	Interactive Response Technology
LDH	Lactate dehydrogenase
m	Meter
MACE	Major Adverse Cardiovascular Events
MAP	Meta-analytic predictive
MedDRA	Medical Dictionary for Regulatory Activities
mg	Milligramm
min	Minute
ml	Milliliter
MCMC	Markov Chain Monte Carlo
MMRM	Mixed effect Model Repeat Measurement
N	Number
PedsQL™	Pediatric Quality of Life Questionnaire™
P-gp	Permeability Glycoprotein
PK	Pharmacokinetic(s)
PopPK	Population Pharmacokinetics
pred	Predicted
PT	Preferred Term
REML	Restricted Maximum Likelihood
REP	Residual Effect Period

Term	Definition / description
RS	Randomised Set
RPM	Report Planning Meeting
SCS	Screened Set
SD	Standard deviation
SE	Standard Error
SEM	Standard Error of the Mean
6MWT	Six-Minute Walk Test
SoC	Standard of Care
SOC	System organ class
SpO ₂	Saturation of oxygen
TMF	Trial Master File
TS	Treated Set
TSAP	Trial Statistical Analysis Plan
ULN	Upper Limit of Normal

WHO-DD World Health Organization Drug Dictionary

3. INTRODUCTION

As per ICH E9 (1) the purpose of this document is to provide a more technical and detailed elaboration of the principal features of the analysis described in the protocol, and to include detailed procedures for executing the statistical analysis of the primary and secondary variables and other data.

This TSAP assumes familiarity with the Clinical Trial Protocol (CTP), including Protocol Amendments. In particular, the TSAP is based on the planned analysis specification as written in CTP Section 7 “Statistical Methods and Determination of Sample Size”. Therefore, TSAP readers may consult the CTP for more background information on the study, e.g., on study objectives, study design and population, treatments, definition of measurements and variables, planning of sample size, randomisation.

[figure not shown]
Unless stated otherwise SAS® Version 9.4 or later will be used for all analyses.

4. CHANGES IN THE PLANNED ANALYSIS OF THE STUDY

[figure not shown]
4.1 ADDITIONS / NEW ANALYSES

In addition to the evaluations depicted in the CTP, the following evaluations will be added:

[figure not shown]
- Secondary endpoint analysis:

- Further endpoint analysis:

4.2 CHANGES

5. ENDPOINT(S)

In this section, more details are given regarding endpoints. Please note that for all endpoints and analyses, [Section 6.7](#) should be consulted for baseline value definition.

Please note, that due to the design of the study, not all time points will be available for all patients.

Handling of missing data points is described in [Section 6.6](#).

For endpoints where the “date of last contact” is utilized, the following will apply:

- The last contact date when the patient was known to be alive is defined as the latest date recorded in the electronic Case Report Form (eCRF) from the dates listed below (in case an Adverse Event date is planned to be imputed for the analysis, the imputed date will also be used for the definition of “date of last contact”):
 - Date of last visit (e.g. for spirometry), date of last reported Adverse Event (AE) (excluding censored dates), date of last reported concomitant treatment, date of last laboratory sample, date of last drug intake, date of last reported dose change / interruption, end of study participation date (as documented on the End of Study eCRF page if the reason for not completing the planned observation period is NOT “Death”), vital status date (from the vital status eCRF page if the patient is known to be alive) and the latest of vital status date / last successful contact date (from the End of Study eCRF page if the patient was lost to follow-up).

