For each patient, the study period is from the signature of the informed consent by the parent(s)/legal guardian until the patient's last visit of the study. Adverse events will be collected during the entire study period and considered treatment-emergent from first study drug intake until 28 days after drug discontinuation.

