5.2.7.2 Adverse event collection and reporting

5.2.7.2.1 AE Collection

The investigator shall maintain and keep detailed records of all AEs in the patient files. The following must be collected and documented on the appropriate CRF(s) by the investigator:

- From signing the informed consent onwards until the individual patient's end of trial: all AEs (serious and non-serious) and all AESIs.
- After the individual patient's end of trial: the investigator does not need to actively monitor the patient for new AEs but should only report any occurrence of cancer and trial treatment related SAEs and trial treatment related AESIs of which the investigator may become aware of by any means of communication, e.g. phone call. Those AEs should be reported on the BI SAE form (see [Section 5.2.7.2.2](#)), but not on the CRF.

Vital Status Data Collection

Patients who discontinue trial medication prematurely, whose parents/legal guardians agree to be contacted further but do not agree to physical visits, should be followed up as described in [Section 3.3.4.1](#), withdrawal from trial treatment. From then on until the individual patient's end of the trial the investigator must report all deaths/fatal AEs regardless of relationship, and trial treatment related SAEs and trial treatment related AESIs the investigator becomes aware of.

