Vital status information

In case of premature discontinuation of trial medication, if the patient does not attend future visits as planned, every attempt will be made to get information on vital status at 24 weeks after randomization, i.e. at the time of data cut-off for the primary analysis, at 52 weeks and at the end of the trial.

Permission to further contacts by site personnel, e.g. by telephone calls, to allow collection of the vital status must be given in the informed consent.

Collection of vital status will be performed in accordance with national ethical and regulatory guidelines.

If death occurs, the investigator will review the circumstances, including the relevant medical records, to ascertain the most likely primary and secondary causes of death. The cause of death will be adjudicated by the AC.

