5.2.2.11 Time to first respiratory-related hospitalization over the whole trial

Time to first respiratory-related hospitalization assessment will be based on the date of hospitalization collected on a specific hospitalization eCRF page.

For those patients who experience a respiratory-related hospitalization, time to first respiratory-related hospitalization [days] will be computed as:

- Date of first respiratory-related hospitalization – date of first drug intake + 1

Patients who did not experience any event during their trial participation will be censored according to the mechanism for censoring as described in [Table 5.2.2.11: 1](#).

Table 5.2.2.11: 1 Censoring Rules for Time to first respiratory-related hospitalization over the whole trial

Rule #	Situation	Outcome (event or censored)	Date of event or censoring
1	Patient had a documented respiratory-related hospitalization and the date of the event is known	Event	Date of event
2	Patient had a documented respiratory-related hospitalization and the date of the event is unknown	Event	Imputed date of event (imputation see Section 6.6.2.2)
3	Patient did not have a documented respiratory-related hospitalization (no matter whether the patient is alive or died or patient status is unknown)	Censored	Date of last contact when the patient was known to be alive and event free

5.2.2.12 Time to first acute Interstitial Lung Disease (ILD) exacerbation or death over the whole trial

For those patients who either experience acute ILD exacerbations or who die due to any cause at any point in the study, time to first acute ILD exacerbation or death [days] will be computed as:

- Date of first documented acute ILD exacerbation or death (whichever occurs earlier) – date of first drug intake + 1

Patients who did not experience any event during their trial participation will be censored according to the mechanism for censoring as described in [Table 5.2.2.12: 1](#).

Table 5.2.2.12: 1 Censoring Rules for Time to first acute ILD exacerbation or death over the whole trial

Rule #	Situation	Outcome (event or censored)	Date of event or censoring
1	Patient had a documented acute ILD exacerbation or died and the date of the event is known	Event	Earliest Date of event

Table 5.2.2.12: 1 Censoring Rules for Time to first acute ILD exacerbation or death over the whole trial (continued)

Rule #	Situation	Outcome (event or censored)	Date of event or censoring

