2	Patient had a documented acute ILD exacerbation or died and the date of the event is unknown	Event	Imputed date of event (imputation see Section 6.6.2.2)
3	Patient did not have a documented acute ILD exacerbation and is alive	Censored	Date of last contact when the patient was known to be alive and event free
4	Patient status is unknown	Censored	Date of last contact when the patient was known to be alive and event free

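### For patients who stop drug and refuse visits, the SAP does not exclude vital-status-only contacts from event-free follow-up for respiratory hospitalisation and for ILD exacerbation or death.

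*SAP*

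**What the plan says.** Protocol 5.2.7.2.1 has a paragraph for patients who stop trial medication early and whose parents "agree to be contacted further but do not agree to physical visits". From that point the investigator "must report all deaths/fatal AEs regardless of relationship, and trial treatment related SAEs and trial treatment related AESIs the investigator becomes aware of". Under protocol 6.2.3, if such a patient does not attend, "every attempt will be made to get information on vital status at 24 weeks after randomization", again at 52 weeks and at the end of the trial.

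Exacerbations are taken from investigator-reported AEs (protocol 5.1.4). Respiratory hospitalisations are taken from a dedicated hospitalisation eCRF page (SAP 5.2.2.11). Neither comes from the vital status page.

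SAP 5 defines the date of last contact once, as the latest of several eCRF dates at which the patient was alive. The list includes the "vital status date (from the vital status eCRF page if the patient is known to be alive"), the end-of-participation date and, for patients lost to follow-up, the last successful contact.

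Table 5.2.2.11: 1, rule 3, censors when "Patient did not have a documented respiratory-related hospitalization (no matter whether the patient is alive or died or patient status is unknown"). Table 5.2.2.12: 1, rule 3, censors when "Patient did not have a documented acute ILD exacerbation and is alive". Both place the censoring at the last contact at which the patient was alive and also event free. The time-to-death table (5.2.2.13: 1) asks only that the patient was alive. SAP 7.5.2.2 reports Kaplan-Meier rates at 24 and 52 weeks by randomised arm and overall.

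**The concern.** Being known to be alive is enough follow-up for time to death. It is not enough for an admission or an exacerbation, because a patient can be alive at week 52 and have had either in the meantime. For this subgroup a non-fatal event judged unrelated to treatment need not be reported, so such a patient has no documented event at any vital-status contact. The censoring rules are triggered by the absence of a documented event, and the only operational date in the SAP rests on being alive. A programmer could therefore carry the patient in the risk set to the vital status date and count time in which events were not being collected. The vital-status contacts fall at weeks 24 and 52, exactly where the rates are read off. Any imbalance in such patients would also appear as a difference between arms.

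**Working it through.** **Reading the text.** Three provisions combine.

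1. Required reporting narrows for this subgroup (protocol 5.2.7.2.1).
2. The date of last contact does not narrow with it (SAP 5).
3. The event-free condition is attached to that date but not defined (Tables 5.2.2.11: 1 and 5.2.2.12: 1).

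Patients who stop drug but keep attending are not affected, since protocol 6.2.3 has AEs, exacerbations and hospitalisations recorded at their visits.

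**Size.** The plan has no figure to reproduce, and every input below is an assumption: a constant hazard, a fraction q of an arm declining visits from week 8 regardless of risk, all of these patients reached for vital status to week 52, and none of their later non-fatal events recorded.

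*Hospitalisation.* Let R be the true 52-week risk and λ = −ln(1 − R)/52. The rate that would be reported at week T is

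(1 − q)(1 − e^(−λT)) + q(1 − e^(−8λ)).

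For R = 0.30, λ = 0.006859 and the risk by week 8 is 5.34%. With q = 0.20:

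- Week 52: 0.8 × 30.0 + 0.2 × 5.34 = 25.1%.
- Week 24 (true 15.2%): 0.8 × 15.18 + 0.2 × 5.34 = 13.2%.

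| True 52-week risk | q = 5% | q = 10% | q = 20% | q = 30% |
|---|---|---|---|---|
| 20% | 19.2% | 18.3% | 16.7% | 15.0% |
| 30% | 28.8% | 27.5% | 25.1% | 22.6% |
| 40% | 38.4% | 36.8% | 33.5% | 30.3% |

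With arms of about 20 and 10 (protocol synopsis) and no true difference at R = 30%, 4 of 20 decliners on nintedanib against 0 of 10 on placebo gives 25.1% against 30.0%. With 1 of 10 on placebo it gives 25.1% against 27.5%.

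*Composite of exacerbation or death.* Deaths remain reportable, so less is lost. Let f be the fraction of the hazard that is fatal, with q = 0.20 and R = 30%. If a death after an unrecorded exacerbation still counts, the recorded 52-week risk in decliners is 1 − e^(−8λ − 44fλ). For f = 1/3 this is 14.4%, and the arm reads 0.8 × 30 + 0.2 × 14.4 = 26.9%. If only deaths that are the first event count, the decliners' figure is 13.6% and the arm reads 26.7%. For f = 1/2 the arm reads 27.7% and 27.5%.

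*Which repair is unbiased for the composite.* Under the same assumptions there are two candidates.

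- Censor all decliners at week 8. The remaining risk set has hazard λ, so the estimate is 30.0%.
- Censor surviving decliners at week 8 but keep those later known to have died. Let D(u) be the probability of death within u weeks after week 8: 1 − e^(−fλu), or f(1 − e^(−λu)) if only first-event deaths count. The estimated hazard is [0.8λe^(−λu) + 0.2D′(u)] / [0.8e^(−λu) + 0.2(D(44) − D(u))]. Integrating from 0 to 44 weeks gives 31.5–31.6% for f = 1/3 and 32.2–32.4% for f = 1/2. The error is upward, because only those who die stay in the risk set.

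**The case against.** The strongest reply is that the safeguard is already there. The two tables require the patient to be event free as well as alive, and the time-to-death table does not. A call that asks only about survival does not show a patient to be event free, so a careful programmer would not use it. This stands as evidence of intent. It does not settle the derivation, because no contact is named as sufficient and the vital status date is not excluded for these endpoints. A reader might infer that the SAP orders vital-status contacts to count as event-free follow-up. It does not; it leaves that reading open.

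A reader might also infer that these events cannot be recorded at all. That is too strong. Protocol 3.1 and the first rule in 5.2.7.2.1 call for all AEs to the patient's end of trial, and the vital-status paragraph sets what must be reported without forbidding more.

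Nor do the documents support a bias in favour of nintedanib. They give no number of decliners and do not say which arm would have more.

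It is tempting to add that AE rates per patient-year are diluted, since AEs are "considered treatment-emergent from first study drug intake until 28 days after drug discontinuation" while reporting narrows at the stop. The effect is capped at 28 days per such patient, and the plan schedules an early end-of-treatment visit and a 28-day follow-up visit with AE review. It does not carry the point.

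Finally, the affected group is probably small, these are descriptive secondary endpoints without a test, and both arms receive nintedanib after week 24. At a 30% rate the binomial standard error is √(0.3 × 0.7/20) = 10.2 points for 20 patients and 14.5 for 10, larger than the errors shown. All of this limits the importance of the point; none of it closes the gap.

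**Conclusion.** The point holds as a gap in the definition of the censoring date. The SAP permits, without requiring, follow-up time to be credited where unrelated non-fatal events were not required to be reported. If it is read that way, both Kaplan-Meier rates are too low, and more so in the arm with more such patients. On the assumptions above, with 20% of an arm declining from week 8, a true 30% becomes about 25% for hospitalisation and about 27% for the composite with one third of events fatal. The 25% figure should not be applied to the composite. These numbers show scale only; the real size depends on how many patients decline, when, and how many of their events go unreported. Neither primary endpoint is affected, and time to death correctly uses the vital status date.

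**What to change.** In SAP 5 and Tables 5.2.2.11: 1 and 5.2.2.12: 1, define a separate censoring date for these two endpoints: the last visit or contact at which AEs and hospitalisations were asked about. State that vital-status-only dates, the last successful contact of patients lost to follow-up and the end-of-participation date do not qualify unless events were asked about then. Keep the present definition for time to death.

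For the composite, censor all such patients at that date in the main analysis. Count later known deaths only in a labelled sensitivity analysis, because counting them while censoring survivors biases the rate upward. Report the number of affected patients per arm.

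The cost is SAP wording and one derived date. Follow-up is slightly shorter and intervals are wider, and deaths after the new date drop out of the main composite analysis, though they remain in time to death. Censoring at this date still assumes that decliners have the same later risk as those who stay, and the report should say so.

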5.1 PRIMARY ENDPOINT(S)

The primary PK endpoint is the $AUC_{\tau,ss}$ based on sampling at steady state (at week 2 and week 26 visit).

For patients receiving nintedanib in Part A, PK profiles on week 2 and week 26 are planned to be collected. For the primary endpoint $AUC_{\tau,ss}$ the $AUC_{\tau,ss}$ at week 2 will be used. If the week 2 value is missing, then it will be replaced by available $AUC_{\tau,ss}$ at week 26 (or later, if PK visit was postponed). For patients receiving placebo in Part A and nintedanib in Part B, $AUC_{\tau,ss}$ evaluated based on

PK profiles at week 26 (or later, if PK visit was postponed) will be used (which corresponds to week 2 on active treatment).

The primary safety endpoint is the N (%) of patients with treatment-emergent adverse events at week 24, i.e., during the planned double-blind period of the trial.

Thus, the number of patients experiencing at least one adverse event during the double-blind period of the trial will be analyzed, see [Section 7.8](#).

5.2 SECONDARY ENDPOINT(S)

5.2.1 Key secondary endpoint(s)

This section is not applicable as no key secondary endpoint has been specified in the CTP.

5.2.2 Secondary endpoint(s)

Endpoints will be used as defined in the CTP Section 2.1.3. Additional specifications are given below.

5.2.2.1 N (%) of patients with treatment-emergent pathological findings of epiphyseal growth plate on imaging at week 24, and week 52

Pathological findings which were already present at baseline imaging will NOT be considered treatment-emergent in this analysis, in spite identified after start of treatment, in order to be able to separate:

- findings that were identified on the follow-up MRI/x-ray and were already present on the baseline MRI/x-ray (i.e. not treatment-emergent)
- findings that were identified on the follow-up MRI/x-ray and were NOT already present on the baseline MRI/x-ray (i.e. treatment-emergent).

There are two possible kinds of predefined pathological findings for the growth plate recorded in the Safety Read Results:

- Pathological Findings at the Distal Femur
- Pathological Findings at the Proximal Tibia

A pathological finding of epiphyseal growth plate is defined as a pathological finding at the distal femur or the proximal tibia.

More precisely,

- Thickening of the epiphyseal growth plates
- Swelling of articular cartilage

will be captured as pathological findings.

Whereas,

- Narrowing of the lucent growth plate margin compared to the baseline time point (at post-baseline time points only)
- Metaphyseal lines
- Other findings

will only be captured as pathological findings if judged pathological.

Frequencies will be reported in a cumulative way over 24 and 52 weeks, respectively.

5.2.2.2 N (%) of patients with treatment-emergent pathological findings on dental examination or imaging at week 24, and week 52

Pathological findings which were already present at baseline imaging/examination will NOT be considered treatment-emergent in this analysis, in spite identified after start of treatment, in order to be able to separate:

- findings that were identified on the follow-up panoramic x-ray and were already present on the baseline panoramic x-ray (i.e. not treatment-emergent)
- findings that were identified on the follow-up panoramic x-ray and were NOT already present on the baseline panoramic x-ray (i.e. treatment-emergent).

For the dental examination, pathological findings will be identified through the dental examination eCRF pages where the question ‘Is this a new abnormal finding’ is answered with ‘Yes’ and thus, an AE page is filled in.

If a baseline pathological finding is reported with a post-baseline worsening, it will be counted as treatment-emergent from the time point of worsening.

For the dental imaging, a pathological finding is defined as at least one tooth being reported in the Safety Read Results with at least one of the following findings:

1. Change in root length (at post-baseline time points only)
 - "Stunted growth (e.g., premature closing of the apex/apices with a blunted root appearance)"
 - "Accelerated growth (abnormally long roots exceeding 2/3rd the total length of the tooth)"
2. Extra/Supernumerary teeth
3. Impacted permanent teeth
4. Additional findings (“cyst present”, “abscess is present”, “solid lesion is present”, “bone abnormality is present”)
5. Additional findings “other findings” (incl. comment)

Frequencies will be reported in a cumulative way over 24 and 52 weeks, respectively.

